### 3 INTRODUCTION

#### 3.1 Background and Rationale

The importance of identifying the patient with ALI or ALF who is likely to die without a liver transplant cannot be overstated and has remained a primary focus of clinical investigation for 25 years. A recent analysis also conducted by the Acute Liver Failure Study Group (ALFSG) found that poor outcomes in the ALI patients are less frequent than is observed in the ALF population. However, in cases where ALI was not related to an acetaminophen (APAP) overdose, progression to poor outcomes was similar: 41% of patients with non-APAP ALI progressed to ALF, transplant and/or death compared to 7% of patients with APAP ALI (1). Unfortunately, analyses have shown that the King's College Criteria (KCC) are inaccurate predictors of prognosis. Clinically based criteria such as the Sequential Organ Failure Assessment (SOFA) and Acute Physiology and Chronic Health Evaluation II (APACHE II) scores offer improved but still inadequate accuracy (2-4). These traditional scoring systems and prognostic models currently used to monitor patients with ALF lack individual sensitivity and specificity and do not provide direct information about the liver's metabolic function, which is a key variable in assessing liver status and potential disease progression versus recovery in ALF patients. The Acute Liver Failure Study Group (ALFSG) completed an analysis of predictors of outcome in the largest cohort ever studied, 1,974 patients, half of whom were randomly assigned to participate in a model development cohort, and half in a validation cohort (5). The ALFSG Prognostic Index (ALFSG-PI) identified coma grade, ALF etiology, vasopressor use, and the log transformations of admission bilirubin and INR as independent clinical predictors of spontaneous survival in patients with ALF, with a c-statistic of 0.84 by AUROC curve analysis. The ALFSG-PI was also significantly better than Model for End-Stage Liver Disease (MELD) score (0.70) or KCC (0.65). The group also developed a prognosis index for ALI patients that identified etiology, admission values of bilirubin, INR, APAP level and duration of jaundice prior to enrollment as variables associated with prediction of progression to ALF, transplant or death within 21 days (1). The ALI prognosis index had a c-statistic of 0.84. Despite these advances, better predictive modalities are still needed.

To more precisely assess the functional reserve of the liver and its capacity to regenerate, we propose to use an actual measure of liver metabolic function, the C-Methacetin Breath Test (MBT; Breath ID®, Exalenz Bioscience Ltd., Modi'in, Israel). MBT is a rapid, reproducible, point-

of-care test of liver metabolic function. After oral or naso-enteric/orogastric tube administration, the  $^{13}\text{C}$  labeled Methacetin is *O*-demethylated by cytochrome P4501A2 in the liver and further biotransformed into  $^{13}\text{CO}_2$ , which is expired in breath. The BreathID® MCS device captures and quantifies expired  $^{13}\text{CO}_2$  and standardizes recovery against expired  $^{12}\text{CO}_2$  through a nasal cannula (in conscious patients) or an adaptor connected to the ventilator line (for intubated patients). The results obtained from the device are expressed as **delta over baseline (DOB)**, which expresses the change in  $^{13}\text{CO}_2/^{12}\text{CO}_2$  ratio in comparison to the baseline measurement. It can be transformed into the **percentage of  $^{13}\text{C}$  dose recovered over time (PDR)** after the ingestion of Methacetin, and the cumulative PDR (CPDR), the rate at which  $^{13}\text{C}$ -Methacetin solution is metabolized, derived from the breath  $^{13}\text{C}/^{12}\text{C}$  ratio.

### **3.2 Summary of BreathID® and MBT Clinical Data**

The BreathID® MBT has been used to assess the functional capacity of the liver in several clinical situations. In a study of 165 patients with cirrhosis which included two ALFSG sites, MBT predicted liver-related death and the appearance/exacerbation of ascites better than the Model for End-Stage Liver Disease (MELD) score (6, copy attached).

MBT has also been used in a pilot study of patients with ALF performed at Kings College Hospital and in Israel (7). Sixty-two patients with severe ALI/ALF of diverse etiologies were followed with the MBT during the acute phase of their illness. During their hospital course, 62% of patients spontaneously survived, 21% underwent liver transplantation, and 18% died with a mean follow-up of 7 days after baseline testing. In patients who spontaneously recovered, admission PDR and CPDR at 20 minutes after Methacetin ingestion were higher than those who died or underwent liver transplantation, with p-value of approximately 0.08 for the difference for both indices. Moreover, in the 38 patients in whom post-admission MBTs were available, PDR20 and CPDR20 were both much higher in spontaneous survivors (SS) than those who died or underwent transplant (p=0.0002 and 0.001, respectively), as were the changes in both parameters between Day 1 and Day 2-4. (The choice of the later day was not standardized. Values were used in the following order of preference depending upon their availability: Day 3, Day 4, or Day 2, if neither Day 3 nor 4 were available). Subgroup analyses clearly showed that patients who died or underwent transplant had similar PDR20 and CPDR20 on Day 1, but both were significantly lower than SS. These data strongly support the hypothesis that the MBT may assess the severity of ALF at

admission and the likelihood of hepatic recovery within 7 days of admission more accurately than laboratory tests regardless of the etiology of liver injury.

**Table 1. Methacetin breath test (MBT) results in 62 patients with ALI/ALF on admission (Day 1) and in 38 patients at one time point after admission (Day 3, or Day 2 or 4 if Day 3 is missing).**

MBT Parameter	Day	N	Total Population	Spontaneous Survivors	Death/ Transplant	P*
			Mean±SD/ Median[range]	Mean±SD/ Median[range]	Mean±SD/ Median[range]	
PDR 20	1	62	2.60[-1.71 - 33.02]	3.31[-1.71 - 13.52]	1.13[-1.22 - 12.80]	0.088
PDR 20	2-4	38	5.05[-1.41 - 28.68]	7.19[0.58 - 28.68]	1.63[-1.41 - 6.11]	0.0002
PDR 20 Delta	1-4	38	3.06±8.29	5.28±8.96	-1.74±3.46	0.013
CPDR 20	1	62	0.52[-0.32 - 5.72]	0.58[-0.29 - 5.72]	0.19[-0.32 - 3.23]	0.079
CPDR 20	2-4	38	1.13[-0.41 - 20.83]	1.54[0.12 - 20.83]	0.46[-0.41 - 1.31]	0.001
CPRD 20 Delta	1-4	38	0.73[-2.10 - 20.32]	0.85[-2.10 - 20.32]	0.0[-1.98 - 1.04]	0.0009

\* ANOVA for normally distributed data; Wilcoxon for non-normally-distributed data. PDR 20, percent dose recovery of CO2 against CO2 in expired breath at 20 minutes after administration of C-Methacetin. PDR 20 Delta refers to the change between Day 1 and post-admission. CPDR 20, cumulative percent dose recovery in expired breath over 20 minutes after administration of C-Methacetin. CPDR 20 Delta refers to the change between Day 1 and post admission. Adapted from (7).

The currently marketed BreathID® Hp System was used in previous clinical trials related to liver applications under IDEs. This system has been modified to allow for longer test duration, resulting in the BreathID® MCS System. The Acute Liver Failure Study Group C-Methacetin Breath Test (ALFSG-MBT) Trial using the BreathID® MCS device will allow several tests of each patient at point-of-care, in real-time, without requiring active patient participation (breath is collected passively). Each patient’s baseline measurement is compared to the Breath Test conducted that day. The objective is to determine if these results reflect improvement or deterioration of liver metabolic function during the course of the disease, which can assist the physician in the management of patients with non-APAP ALI or ALF.

Since current treatments used to stabilize and care for patients with ALI and ALF may obscure the main parameters used to delineate the prognosis (i.e., INR, bilirubin, grade of hepatic encephalopathy and renal/metabolic status), the MBT may show superiority over the current prognosis models. For example, INR interpretation can be confounded by blood products administered to a patient or may be impacted upon by a variety of medical interventions, such as disseminated intravascular coagulation (DIC); in contrast, the MBT is not affected by blood product administration or development of DIC. Additionally, MBT monitoring could be potentially performed every 24 hours over the patient's course in the Intensive Care Unit (ICU), providing dynamic data that may show earlier changes than routine blood tests, since it measures directly the immediate metabolism of the test substrate, as opposed to assessing the presence of blood components that have accumulated over a greater period of time, such as total bilirubin levels.

### **3.3 BreathID® C-Methacetin Breath Test (MBT) System Description**

The C-Methacetin Breath Test (MBT) is a non-invasive test for assessing liver metabolic function in order to aid in management of patients with non-APAP ALI or ALF. The BreathID® MCS System consists of the BreathID® MCS device and a test kit containing a breath collection cannula and a non-radioactive isotope C-Methacetin solution. It measures and computes the ratio between CO2 and CO2 in the patient's exhaled breath. The MBT System has inherent design features and accessories for this indication including a small footprint and portability for deployment in an ICU environment.

The components of the MBT system include the (1) BreathID® MCS unit; (2) Cannula; and the (3) C-Methacetin solution. A dedicated flash memory stick for automatic raw data download will be provided to all participating investigative sites. All components of the MBT system will be provided by Exalenz Bioscience Ltd., and a representative from Exalenz will provide the initial on-site training to the study team at each investigative site.

#### **3.3.1 BreathID® MCS Unit**

Exalenz Bioscience Ltd. has developed a molecular correlation spectrometer, based on specific optical-radiation emission and absorption by CO2 and CO2 gases. This device continuously senses exhaled breath and analyzes CO2 in real-time through a breath collection cannula connected to the patient. Based on Molecular Correlation Spectrometry (MCS), the BreathID® MCS device

continuously measures  $^{13}\text{CO}_2$  and  $^{12}\text{CO}_2$  concentrations from the patient's breath and establishes the  $^{13}\text{CO}_2/^{12}\text{CO}_2$  ratio. The cannula continuously transports the breath sample from the patient to the BreathID® MCS device. Depending upon the status of the patient, the cannula may be nasal (for conscious patients) or an adaptor may be used for connection to the respiratory line (for intubated patients). Results are displayed in real time on the device screen and are printed after the completion of the test. The BreathID® MCS device calculates the delta over baseline (DOB), which can be translated into the percent dose recovery (PDR) and the cumulative percent dose recovery (CPDR) for each time point derived from the ratio difference compared to baseline (normalized/adjusted to the patient's body weight and height as well as test substrate dose) throughout the course of the Breath Test. The maximum value of the PDR is called the PDRPeak. The  $^{13}\text{C}$ -Methacetin metabolism begins almost immediately since liquid passes through the stomach to the duodenum, where it is absorbed, without delay. The default breath collection test time is one hour after ingestion of  $^{13}\text{C}$ -Methacetin solution.

The light sources are  $^{13}\text{CO}_2$  and  $^{12}\text{CO}_2$  discharging lamps. By using  $^{13}\text{CO}_2$  and  $^{12}\text{CO}_2$  discharging lamps as light sources, light absorption will be solely due to the existence of  $^{13}\text{CO}_2$  and  $^{12}\text{CO}_2$  in the gas mixtures. Furthermore, by using  $^{13}\text{CO}_2$  and  $^{12}\text{CO}_2$  discharging lamps as light sources, background radiation will be substantially reduced, leading to highly sensitive absorption curves. These highly sensitive absorption curves enable detection of very small variations in  $^{13}\text{CO}_2$  and  $^{12}\text{CO}_2$  concentrations and the  $^{13}\text{CO}_2/^{12}\text{CO}_2$  ratio. The BreathID® MCS System can detect variations of less than 1/1000 in the  $^{13}\text{CO}_2/^{12}\text{CO}_2$  ratio measurement.

The actual breath collection is automatically done by the device and is not operator dependent. If the patient is not connected properly (e.g. the breath does not reach the device), the BreathID® MCS device will prompt the operator to adjust the cannula.

### **3.3.2 Cannula**

There are two test kit options included in the kit; one containing a breath collection cannula with nasal prongs to be used for breath collection in non-intubated/conscious patients, and the other containing a cannula that has an airway adapter to facilitate connection to the respiratory line in intubated patients. The cannula transports the breath sample from the patient to the BreathID® MCS device. The cannula test kit is a single-use kit and is comprised of a plastic sampling line

with an in-line hydrophobic filter (used to reduce the amount of moisture present from the patient's breath) and a Luer-lock connector for connection to the BreathID® MCS device.

Most subjects arriving at the ICU with ALF are unconscious and intubated. As patient status improves and the patient is removed from the respirator, the nasal cannula can be used to capture breath while they are spontaneously breathing. Both types of cannulae are necessary so as to enable regular monitoring and trending of results as patient's status changes during their stay in the ICU. No significant difference in measurements is expected between those captured by the intubated or the nasal cannulae, since the internal capnograph-like instrument of the device automatically sorts out the breath collected and allows through the system only the end tidal portion of the breath exhaled. The device is designed to accommodate an extended range of respiratory rates.

### **3.3.3 C-Methacetin Solution**

Exalenz Bioscience Ltd. will supply a ready to use, non-radioactive isotope C-Methacetin solution for single-use oral administration (75 mg in 150 ml purified water), dispensed in thermoplastic polyester (PTE) bottles sealed with a plastic child resistant stopper. The C-Methacetin solution can be administered through a feeding tube (used in standard ALF patient management), as well as via typical oral administration for ALI and ALF patients able to ingest the test substrate orally. C-Methacetin meets all of the qualifications for a liver function test substrate: it is a nontoxic small molecule; is administered orally; is rapidly absorbed; and is exclusively metabolized by the liver. Furthermore, C can be easily synthesized into a key location within this molecule. No related serious adverse events have been reported when using this substance, including in vulnerable populations, and the compound remains stable over time.

The C-Methacetin solution is a well-known diagnostic reagent that has been described in the literature and used for over 30 years by researchers around the world (8-10). C-Methacetin is rapidly absorbed and metabolized by the hepatic mixed function oxidase, via O-demethylation. This process is carried out by hepatic cytochrome P450 enzymes that produce two products, acetaminophen and formaldehyde, which is transformed through two successive oxidative steps to CO2.

Toxicology testing results in animals and other clinical information support the safe use of Methacetin in humans. Based on the acute toxicity studies in mice and rats where relatively high

LD50 values of 1190mg/kg were administered, the Methacetin dose administered in human breath tests in adults of 75 mg, or approximately 1mg/kg, has a safety ratio in excess of 1000-fold (11). There have been no reports of any complications with the use of this substance in over 2500 patients tested worldwide (see IDE filing). The main metabolite of Methacetin is acetaminophen which has wide routine clinical use at much higher doses than orally administered dose of C-Methacetin of 75mg used in this study. Testing of sera after exposure to 75mg C-Methacetin in 23 ALF patients at King's College disclosed no increase in serum acetaminophen-cysteine adducts that would suggest further hepatocyte injury due to the C-Methacetin (12).

Many studies using C-Methacetin for liver function assessment have been published. Representative references have been cited that support the conclusion that C-Methacetin solution is a "safe" test substrate and that it has been used on high-risk population groups such as the elderly, neonates or pregnant women, and patients with cirrhosis (13-16). This provides further assurance that C-Methacetin is appropriate to use in breath tests intended for liver function assessment.

## **4 OBJECTIVES AND ENDPOINTS**

### **4.1 Primary Objective**

The primary aim of the study is to assess the relationship between Day 1 PDRPeak values and Day 21 spontaneous survival in patients with ALF or non-APAP ALI. This outcome requires only one measurement per subject and examines whether the distributions (means) of enrollment PDRPeak values vary between those that spontaneously survive at Day 21 and those that either die or get a transplant by Day 21.

### **4.2 Endpoints**

#### **4.2.1 Primary Endpoint**

- The primary end-point of the study is PDRPeak at Day 1 that will be treated as a continuous variable.

#### **4.2.2 Secondary Endpoints**

1. Using the Day 1 PDRPeak as a continuous variable, we will determine a cut point value that best distinguishes between those that do and do not spontaneously survive at Day 21.

2. There are several exploratory aims that will be conducted for future hypothesis generation. These analyses include: assessing the change in MBT measurements (CPDR20, PDRPeak, PDR20 and CPDR30) over a maximum of 7 days from enrollment; assessing the relationship between single time points of MBT measurements (PDRPeak, PDR20 and CPDR20) and clinical outcome (both early and late outcomes, Day 7 and Day 21 SS); and, evaluating the use of the PDRPeak as a prognosis for Day 7 and Day 21 SS either alone or in conjunction with other clinical parameters including etiology, laboratory measurements and other available prognostic indices.

### 4.2.3 Safety Endpoints

The administration of Methacetin (75mg/dose) results in the generation of acetaminophen (75mg/dose), and therefore presents a modest safety concern in patients with ALF, particularly in those with APAP overdose. Use of NAC in patients admitted with APAP overdose or non-APAP ALF should obviate minor adverse effect potential of this small dose. In a retrospective study, sera from ALF patients who were given the C-Methacetin MBT at King's College were assayed for presence of acetaminophen adducts. Participants of this study received MBT daily up to 7 days. No *de novo* appearance of adducts was observed for non-APAP subjects, nor was there an increase in adduct levels in acetaminophen toxicity subjects.

To confirm the safety profile of the MBT, a prospective safety sub-study is planned for this protocol as outlined in Section 10.1. This safety sub-study will include determining APAP and APAP-adduct concentrations in sera from study participants with ALF immediately prior to each administration of the C-Methacetin solution. A positive safety endpoint is defined as:

1. the absence of decline in APAP or APAP-adduct concentration between two consecutive determinations for patients with ALF due to APAP overdose;
2. presence of a significant (toxic quantity,  $\geq 1 \mu\text{mol/L}$ ) APAP-adducts in patients with non-APAP ALF;
3. adjudicated cases where APAP (non-adduct, parent compound) is detected in the serum of a patient with non-APAP ALF. It should be noted that in some instances, APAP appears to be detected in patients with non-APAP ALF if the total bilirubin is  $\geq 10 \text{ mg/dl}$ ; these are considered false-positive due to the cross-reactivity between APAP reactants and bilirubin in some colorimetric APAP assays (Polson, et al.). Such cases of detectable APAP in patients with non-APAP ALF will be adjudicated on an individual basis by the study's appointed

independent Medical Safety Monitor to determine the likelihood of Methacetin toxicity. Results of adduct testing will initially be reviewed internally and forwarded in real time to the MSM for review. These data will then be reported in summary fashion to the DSMB.

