### **8.2 Administration of the Breath Test**

The Breath Test will be performed up to five times during the study period on all enrolled subjects. The first Breath Test will be performed as close to the time of study enrollment as possible upon admission into the study (Day 1). The Breath Test will be repeated on Days 2, 3, 5 and 7 as close as possible to the same time of day as the first Breath Test. If a subject who is enrolled into the ALFSG-MBT Trial with ALI converts to ALF, breath test collection will continue until a maximum of five Breath Tests have been performed. Once the ALI subject has been enrolled into the ALFSG Registry with ALF, subsequent Breath Tests should be performed as close to the same time of day as the first Breath Test. If an enrolled ALI or ALF subject receives a liver transplant,

is discharged/transferred from the hospital or dies prior to Day 7, no additional Breath Tests will be performed.

The following characteristics will be collected on each day of the MBT before administration of test substrate:

- The mechanism of ventilation (spontaneous or mechanical);
- Route of administration of test substrate (by mouth or by naso-enteric or orogastric tube);
- Location of the distal end of the naso-enteric tube (intra-gastric or intra-duodenal) or orogastric tube;
- Concurrent use of vasopressors, acyclovir, famotidine and statins;
- Last meal or tube feeding;
- Subject's weight;
- Concurrently administered medications, including NAC; and
- Use of renal replacement therapy during the MBT.

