### **8.2.1 Requirements for Administration of Test Substrate**

#### 1. Fasting

Subjects will perform the breath test once enrolled into the trial and when the following criteria have been met:

- Protocol-specified labs are completed prior to the administration of the test substrate.
- *Oral administration of test substrate:* The subject should be fasting from solid food for a minimum 6 hours and from oral medications for a minimum of 1 hour.
- *Naso-enteric and orogastric tube administration of test substrate.* In subjects who are receiving tube feeding, feeding should be discontinued for a minimum of 4 hours. Gastric contents should be aspirated prior to the instillation of C-Methacetin solution *via* the naso-enteric or orogastric tube.

Feeding may be resumed after the MBT has been completed (*i.e.*, at 60 minutes after administration of the test substrate).

2. Subject has not ingested acetaminophen-related medications (e.g. Tylenol) within the past 24 hours (subjects with acetaminophen intoxication may be included 24 hours after ingestion).
3. Subject has not received general anesthesia in the last 24 hours. This does not include appropriate utilization of sedative and analgesic drugs for subjects within a critical care

environment, such as propofol sedation or sedation related to liver biopsy. In those instances, all enterally and parenterally administered medications will be recorded in the study CRF.

4. Evidence of ileus or presenting with contra-indication to administration of oral drugs.
5. The MBT should not be performed in cases where there is a suspicion that aspiration may occur.
6. Subjects who require RRT (intermittent and continuous) after enrollment into the study will not be excluded; however, it is preferred that the test substrate and Breath Test are not administered during dialysis treatments.

**Note:** Subjects with gastroparesis may be included as the delayed emptying has negligible impact on fluids (17). The presence of evidence of delayed gastric emptying and/or ileus should be noted on the CRF for further analysis to show that the impact is negligible for MBT measures. Naso-enteric and orogastric tubes should be clamped for 10 minutes after administration of the C-Methacetin solution.

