#### **8.3 Performance of the APAP Adduct Assays and APAP Concentration Assays**

Serum for acetaminophen (APAP) and APAP-adduct levels will be collected with routine morning labs on each day from Day 2-7, as well as Day 1 as a baseline value, from the first 20 ALF subjects enrolled. Serum samples will be reserved for the sole purpose of determining whether APAP or APAP-adducts accumulate during repeated administrations of the C-Methacetin solution in patients with ALF. The collected samples will be shipped to and analyzed by [name] at the University of Arkansas.

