## 8.5 Schedule of Assessments

	Screening/ Subject Enrollment	Day 1	Day 2	Day 3	Day 5	Day 7	Day 21
Demographics	X						
Medical History	X						
Confirm Eligibility Criteria ^	X						
Prior Medications	X						
Concomitant Medications		X	X	X	X	X	
Grade of HE	X	X	X	X	X	X	
Labs (lactate, bicarbonate, INR, total bilirubin, phosphate, Creatinine, WBC, Platelet count, ammonia-arterial or venous (if clinically indicated))		X	X	X	X	X	
RRT (record time/tx prior to MBT)		X	X	X	X	X	
MBT		X	X	X	X	X	
Serum for APAP and APAP-adduct levels*		X	X	X	X	X	
AE Reporting		X	X	X	X	X	(SAEs only)
End of Study							X
Collection of data for MELD, KCC, and ALFSG- PI	X	X	X	X	X	X	

\* Only in the first 20 consecutive ALF subjects enrolled

^ In women of child-bearing potential; Urine pregnancy test or blood human chorionic gonadotropin (hCG) is acceptable.

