## **10 SAFETY AND ADVERSE EVENTS**

### **10.1 Safety Sub-study**

The safety of the MBT has been demonstrated in several clinical applications. However, the repeated administration of the test substrate, which represents the equivalent of 75 mg of APAP per administration, will be closely monitored to ensure that this small dose of APAP will not result in additional liver injury (particularly in the presence of NAC). The results of the Retrospective Safety Study were examined before enrollment in the prognosis study began, as outlined in Section 4.2.3 of this protocol. A second, prospective safety study will be performed and sera collected from the first 20 ALF subjects enrolled into the ALF-MBT Trial as described herein, in whom we propose to administer MBT on Day 2, 3, 5, and 7 unless the subject is discharged/transferred, transplanted or dies. Serum for acetaminophen (APAP) and APAP-adduct levels will be collected with routine AM labs on each day from Day 2-7, as well as Day 1 as a baseline value. Serum samples will be reserved for the sole purpose of determining APAP or APAP-adducts levels in patients with ALF during repeated administrations of the C-Methacetin solution and will be performed by [name] at the University of Arkansas for Medical Sciences, Little Rock, AR.

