### **10.2 Adverse Events**

Adverse event reporting and procedures are described in detail in the MOP.

In the ALFSG-MBT Trial, any medical conditions not present prior to the initial administration of the test substrate but that emerge after the initial test substrate is administered are considered AEs. Adverse Events encountered from Day 1 through Day 7 of the study period will be recorded, and Serious Adverse Events from Day 1 through the Day 21 of the study period will be recorded.

Designated study personnel at all investigative sites are responsible for entering any and all non-serious and serious adverse events, regardless of severity or relationship to the C-Methacetin solution and device, and including updates to adverse event information (e.g., date of resolution, action taken) as needed, into the WebDCU™ database within timelines defined in the MOP and in the subject's source documents. Upon data submission of the SAE eCRF, the system will trigger an automatic e-mail notification to the independent Medical Safety Monitor (MSM) stating that an SAE has occurred. The MSM will access the information via the password protected web based system for review and report safety concerns to the DSMB.

Adverse events will be defined and severity graded according to the Common Terminology Criteria for Adverse Events (CTCAE) found in the MOP. AEs will be submitted online through WebDCU™ and coded centrally into standard terminology using AEs will be using the Medical Dictionary for Regulatory Activities (MedDRA). Guidelines for report content and structure are provided in the MOP.

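### No scheduled APAP, adduct or protocol laboratory measurement follows the Day 7 (fifth) methacetin dose, and non-serious AE collection ends the same day

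*Combined protocol and SAP*

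**What the plan says.** **Dosing.** Section 8.2 allows up to five breath tests. The first is on Day 1, and the later ones are set out as follows: "The Breath Test will be repeated on Days 2, 3, 5 and 7 as close as possible to the same time of day". The fifth dose therefore falls on Day 7. Section 10.1 equates each administration with 75 mg of APAP.

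**Timing of samples relative to dose.** Section 4.2.3 places the sub-study serum "immediately prior to each administration of the" methacetin solution. Section 8.2.1, item 1, adds a condition for giving the substrate: "Protocol-specified labs are completed prior to the administration of the test substrate".

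**Days sampled.** Section 8.3 has APAP and adduct serum "collected with routine morning labs on each day from Day 2-7, as well as Day 1 as a baseline value", and section 10.1 says the same in nearly the same words ("will be collected with routine AM labs on each day from Day 2-7, as well as Day 1 as a baseline value"). The schedule in section 8.5 marks this serum on Days 1, 2, 3, 5 and 7 only, with the footnote "Only in the first 20 consecutive ALF subjects enrolled". It has no laboratory or serum entry after Day 7. The Safety Analysis row of the synopsis also ends the standard laboratory tests, liver biochemistry included, at seven days.

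**Purpose.** Section 8.3 reserves the sera for "determining whether APAP or APAP-adducts accumulate during repeated administrations" of the solution.

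**Clinical follow-up.** Section 10.2: "Adverse Events encountered from Day 1 through Day 7 of the study period will be recorded". SAEs are recorded to Day 21, and the Day 21 contact (sections 5.1 and 8.1) also asks about survival and transplantation.

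**The concern.** A sample drawn before a dose says nothing about that dose. It reports on the doses already given. When the last planned sample and the last planned dose share a day, and the sample comes first, the last dose goes unobserved in the serum data.

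This matters because all three positive safety endpoints in section 4.2.3 are defined on serum APAP or adducts. With no later sample, the fifth dose cannot trigger any of them. SAEs, deaths and transplants to Day 21 are a weak substitute: they are not serum measures, and in acute liver failure they are also outcomes of the disease itself. Section 10.1 undertakes to watch repeated administration closely for added liver injury, yet the full course as planned is the one exposure level without a scheduled biochemical reading.

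**Working it through.** No sample size, power or alpha enters here, and the plan gives no figure to reproduce. The check matches dosing days to later sampling days.

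**Inputs**
- Dosing days: 1, 2, 3, 5, 7 (section 8.2).
- Sampling days, reading A: 1, 2, 3, 5, 7 (section 8.5, consistent with the before-each-dose rule in 4.2.3).
- Sampling days, reading B: 1, 2, 3, 4, 5, 6, 7 (sections 8.3 and 10.1).
- A sample on a dosing day precedes that day's dose (sections 4.2.3 and 8.2.1). Sections 8.3 and 10.1 say only that serum goes with the morning labs, so the order rests on the other two sections.
- Dose: 75 mg per administration (sections 4.2.3 and 10.1).

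**Rule.** Later samples for a dose on day d = number of sampling days greater than d.

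| Dose | Day | Next sample, A | Later samples, A | Next sample, B | Later samples, B |
|---|---|---|---|---|---|
| 1 | 1 | Day 2 | 4 | Day 2 | 6 |
| 2 | 2 | Day 3 | 3 | Day 3 | 5 |
| 3 | 3 | Day 5 | 2 | Day 4 | 4 |
| 4 | 5 | Day 7 | 1 | Day 6 | 2 |
| 5 | 7 | none | 0 | none | 0 |

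**Exposure behind the last sample.** Planned total: 5 × 75 = 375 mg. Given before the Day 7 sample: 4 × 75 = 300 mg. Covered: 300/375 = 80%. Not covered: 75/375 = 20%, or one dose of five. Both readings agree.

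**Clinical windows after the fifth dose.** Non-serious AEs: the remainder of Day 7 and no further day. SAEs, death and transplantation: 21 − 7 = 14 further days.

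**With one added sample.** Any APAP/adduct sample after the Day 7 dose raises coverage to 5 of 5 doses, 375 of 375 mg.

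**Side finding.** The two readings are not the same plan: B includes Days 4 and 6, A does not. If section 4.2.3 is taken literally (serum only before a dose), a subject who receives k doses has k samples, and the last of them reflects k − 1 doses, whatever the day of stopping. Daily sampling avoids this for doses 1 to 4 while the subject remains under sampling, but not for dose 5.

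**The case against.** The strongest reply is that little is lost. Four points deserve weight.

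1. **Clinical follow-up does not stop at Day 7.** A reader might infer that the effect of the fifth dose is never measured at all. The documents do not support that: SAEs, death and transplantation are followed for 14 further days, and a non-serious event later on Day 7 is recordable. What is missing is scheduled biochemistry and later non-serious events.
2. **Accumulation is already tested.** The closest dosing is on Days 1, 2 and 3, and samples follow it. Doses 4 and 5 each come two days after the one before. Milligrams given are not serum concentration, and nothing in the documents gives a kinetic reason to expect a new signal after dose five that was absent after doses 1 to 4. This stands, and it limits how much the gap matters.
3. **There is supporting evidence.** Section 4.2.3 describes a retrospective study with testing daily for up to seven days and no adduct signal; section 3.3.3 gives 23 ALF patients. This helps only in part. The documents do not say how many patients had all the doses or whether sera were taken after the last one, and the prospective sub-study exists to confirm that result.
4. **The endpoints can be evaluated as written.** One might infer that endpoint item 1 fails for the last dose. It compares two consecutive determinations, is not defined per dose, and applies only to APAP-overdose ALF; items 2 and 3 need a single value. It is also not stated anywhere that a five-dose conclusion will be claimed.

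Two further limits apply. Section 8.4 says subjects also have laboratory tests under the ALFSG Registry, whose duration is not given, so liver tests after Day 7 may exist outside this schedule. AE procedures are detailed in a Manual of Procedures that is not available here.

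**Conclusion.** The gap is real and narrow. Under either sampling schedule, no scheduled APAP, adduct or protocol laboratory value follows the Day 7 dose, and non-serious AE collection ends that day. For a subject who receives that dose, the serum endpoints cover at most four of five administrations.

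The conclusion assumes that the Day 7 serum is drawn before the dose, as sections 4.2.3 and 8.2.1 require, and that no unseen procedure adds a later sample.

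It reaches only subjects still being tested on Day 7. Testing stops at transplant, discharge, transfer or death (section 5.1) and may stop for other reasons (section 9.2). The number of the 20 sub-study subjects who reach dose five is not stated and could be anywhere from 0 to 20, so it would be wrong to infer that all are affected. The sub-study still addresses repeated dosing through dose four, and the primary analysis is untouched. The change is worth making because it is cheap and lets the serum endpoints register the last dose.

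**What to change.** - **Sections 8.3, 8.5 and 10.1:** add one APAP/adduct sample with the next routine morning labs (Day 8) for sub-study subjects who received the Day 7 dose and are still in hospital. Adjust section 4.2.3 to match.
- **Sections 10.2 and 8.5:** continue non-serious AE collection through Day 7 or to a fixed period after the last administration (for example 24 hours), whichever is later, so that nobody's present window is shortened. Record standard-of-care liver tests from that period where they are drawn.
- **Same edit:** reconcile the sampling days, which are daily on Days 1 to 7 in sections 8.3 and 10.1 but before each dose, or Days 1, 2, 3, 5 and 7, in sections 4.2.3 and 8.5.

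The cost is one extra tube in at most 20 in-patients and about one more day of AE entry for subjects tested on Day 7. A sentence limiting the accumulation conclusion to four administrations would cost nothing and prevent over-reading, but it would leave the last dose unobserved.
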